RESEARCH PROTOCOL

TITLE

**Effects of vitamin D₃ supplementation on lung functions and
exercise tolerance in D₃ deficient Asthma COPD Overlap
(ACO) patients**

Date:06/09/2018

Project Summary

Background: Asthma COPD Overlap (ACO) has been described as a distinct disease now-a-days. Several studies have shown positive relationship between serum concentration of 25 hydroxyvitamin D, lung function and exercise tolerance in different group of patients. However, vitamin D supplementation showed significant improvement in lung function status and exercise tolerance in both asthma and COPD patients but no study was found in ACO patients. **Objectives:** To evaluate the effects of vitamin D₃ supplementation on lung function status and exercise tolerance in D₃ deficient, stable patients with ACO. **Methods:** This double blinded placebo controlled trial will be conducted by Department of Physiology Bangabandhu Sheikh Mujib Medical University (BSMMU), Shahbag, Dhaka from March 2018 to February 2019. For this study a total number 70 vitamin D₃ deficient (serum 25 hydroxycholecalceferol <30 ng/ml) male, stable (diagnosed patient, who was not experienced any acute exacerbation, hospitalization, urgent care visits or changes in routine medication within 4 weeks prior to study) patients with ACO of age 40-70 years will be selected. They will be selected from the Out Patient Department (OPD) of the National Institute of Diseases of Chest and Hospital (NIDCH) and will be randomly grouped as A (control) and B (study). All the participants will be matched in terms of age, duration of ACO, duration of smoking, body mass index (BMI), mid upper arm circumference (MUAC), waist hip ratio, occupational status, socioeconomic status, serum

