Is there any improvement in lung function status and exercise tolerance in vitamin D₃ deficient ACO patients after having vitamin D₃ supplementation?

Hypothesis

Null: Vitamin D₃ supplementation does not improve lung functions and exercise tolerance in vitamin D deficient ACO patient.

Alternate: Vitamin D₃ supplementation improves lung functions and exercise tolerance in vitamin D deficient ACO patient.

Objectives:

General objectives:

To evaluate the effects of vitamin D₃ supplementation on lung function status and exercise tolerance in D₃ deficient, stable patients with ACO.

Specific objectives

- To measure the FVC, FEV₁, FEV₆, FEV₁/FVC%, PEFR and FEF_{25-75%} of vitamin D₃ deficient, stable patients with ACO, in order to assess their lung function status at baseline.
- To measure the 6MWD of all the patients, in order to assess their functional exercise capacity at baseline.
- To measure the SpO₂ at rest of all the patients, in order to assess the basal oxygenation status at baseline.
- To measure the level of dyspnea and fatigue at rest of all the patients in order to assess the basal breathlessness level at baseline.
- To measure the both the SpO₂ and level of dyspnea and fatigue again after 6MWT, for the assessment of their exercise tolerance at baseline.
- To measure the all these variables in study group at 13th weeks and at 26th weeks of their follow up.
- To measure the all these variables in control group at 13th weeks and at 26th weeks of their follow up.
- To compare all these variables in study group at baseline and endline.
- To compare all these variables in control group at baseline and endline
- To compare all these variables in both group at baseline and endline.

Methods

Type of study	: Double blinded placebo controlled trial
Place of study	: Department of Physiology, Bangabandhu Sheikh Mujib Medical University (BSMMU), Shahbagh, Dhaka
Period of study	: March 2018 to February 2019
Study population	: Stable patients of ACO with vitamin D ₃ deficiency
Sample size	: 60
Sampling	: Consecutive sampling
Grouping	:
Group A (Control)	: 30 (thirty) D ₃ deficient ACO patients with placebo administration
Group B (Study)	: 30 (thirty) D ₃ deficient ACO patients with vitamin D ₃ administration

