For the assessment of all the variables of all the patients on day 0, at 13th week and as well as at 26th week, they will be designated as A₀, A₁ and A₂ (control) and B₀, B₁ and B₂ (study). In addition, for the mean of SpO₂, level of dyspnea and level of fatigue at resting condition (before 6MWT), all the groups will be further designated as A_{0before}, A_{1before}, A_{2before}, B_{0before}, B_{1before} and B_{2before} respectively. Similarly after 6MWT all these six subgroups will be again designated as A_{0after}, A_{1after}, A_{2after} and B_{0after}, B_{1after}, B_{2after}, for measurement of these three variables.

Sample size calculation

Using the following statistical formula

$$n = [(Z\alpha + Z\beta)^2 \times (\sigma_1^2 + \sigma_2^2)] / (\mu_1 - \mu_2)^2$$

(Kirkwood and Sterne 2003)

$$\text{Mean of control, } \mu_1 = 364.1$$

$$\text{Mean of study group, } \mu_2 = 357.3$$

$$\text{SD of control, } \sigma_1 = 7.21$$

$$\text{SD of study group, } \sigma_2 = 12.25$$

(Hassan 2018)

$$\text{Type I Error, } Z\alpha = 1.96$$

$$\text{Type II Error, } Z\beta = 0.84$$

(Kirkwood and Sterne 2003)

Therefore,

$$\begin{aligned} n &= [(Z\alpha + Z\beta)^2 \times (\sigma_1^2 + \sigma_2^2)] / (\mu_1 - \mu_2)^2 \\ &= [(1.96 + 0.84)^2 \times (7.21^2 + 12.25^2)] / (364.1 - 357.3)^2 \\ &= [7.84 \times (51.9841 + 150.0625)] / (6.8)^2 \\ &= 1584.04534 / 46.24 \\ &= 34.2570359 \\ &= \text{approximately 35 for each group.} \end{aligned}$$

Subject selection:

Inclusion criteria

- Pulmonologist diagnosed stable patient of ACO
(GINA and GOLD 2015)
- Duration of ACO: > 4 year
- Vitamin D₃ deficient : Serum 25(OH)D <30 ng/ml
(Vitamin D Council 2017)
- Age: 40 -70 years
- Sex: Male
- Socioeconomic status: middle class
- Smoker
- Anthropometric status:
 - BMI=18.6-24.9 kg/m²
(WHO 2006)
 - mid upper arm circumference>25.1 cm
(Sultana et al. 2015)
 - waist-hip ratio<0.89
(Sultana et al. 2015)
- Serum parathormone: 10-65 pg/ml
- Serum Ca²⁺: 8.5-10.5 mg/dl
- Serum PO₄³⁻: 2.3-4.7 mg/dl
- Serum alkaline phosphatase: 30-120 U/L
- SGPT: <50 U/L
- Serum creatinine: 0.7-1.3 mg/dl
- FBS: 3.5-6.1 mmol/L
- Serum HbA1c: 4.5-6.3 %

- Serum cholesterol: <200 mg/dl
- Serum HDL: >40 mg/dl,
- Serum LDL: <130 mg/dl
- Serum TG: <150 mg/dl

Exclusion criteria

With history of:

[figure not shown]
- any other pulmonary diseases, as,
 - ✓ chronic obstructive pulmonary disease
 - ✓ bronchial asthma
 - ✓ respiratory tract infection
 - ✓ bronchiectasis
 - ✓ pleural effusion
 - ✓ tuberculosis

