With these, all patients of both the groups will be advised to continue ad lib (according to their own choice) diet as well as to have sunlight exposure (within 10 am to 2 pm) only for 20 minutes daily (Manjeeta 2016).

In the mean time, a good rapport will be built up to take time to time follow-up over telephone and visiting patient's place with scheduled appointment to maintain a proper follow up at 1st (day 1) 2nd (at 13th week) and 3rd (at 26th week) visit of the study , in addition to the hematological values.

Any patient, who will be failed to follow the study procedure exactly during study period, will be dropped and a new one will be included to fulfill the desired total sample number.

Test procedure for spirometry

(Hassan 2018)

- At first, the subject will be asked to take rest sitting on a chair and remain calm and quiet for 5 minutes.
- The detailed procedure will be explained to him to ensure his maximum cooperation.
- The switch of spirometer will be on and windows will be open.
- Patients' information will be filled up and saved.
- The patient will be asked to hold a disposable paper mouthpiece (connected to spirometer) in his hand horizontally and to place it in between his two lips.
- To make good seal, he will also be asked to put the lips tightly around the outside of the mouthpiece.
- Then he will be asked to inhale first as deeply and as rapidly, as possible, which was followed by a forceful expiration for the possible longest period into the mouthpiece.
- The readings of different variables will be recorded from the spirometer monitor.
- Three (3) consecutive readings at 5 minutes interval for each parameter will be taken and the best value will be noted.

Test procedure for pulse oximetry

(Hassan 2018)

- The patient will be asked to take rest and remain calm and quiet for 10 minutes (MacAllister et al. 2007).
- The detailed procedure will be explained to him to ensure his maximum cooperation.
- Then his right index finger will be washed with alcohol and pulse oximeter sensor will be applied.
- The switch button will be on.
- The reading will be recorded from the display screen.
- Three (3) consecutive readings at 5 minutes interval will be taken and the best value will be noted.

Procedure for six minute walk test (6MWT)

(Hassan 2018)

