The 6MWT will be performed at indoors, along a long, flat, straight, enclosed corridor with a hard surface that was seldom traveled. The walking course will be 30 meter in length which was marked every 3 meter. The turnaround points will be marked with a cone. A starting line, which marked the beginning and end of each 6 meter lap, will be marked on the floor using brightly colored tape.

The subject will be asked to walk at his own maximal pace along the corridor from the end, covering as much ground as he can, during the allotted time, without running. He will be also advised to take rest if he

was too exhausted to continue the test. Standard phrases at regular intervals (every 60 seconds) will be used, like: “you are doing well,” “keep up the good work”. At the same time he will be also informed about the past time and how much left before the test completed.

If any of the subjects develop chest pain, intolerable dyspnea, leg cramps, staggering, diaphoresis or pale appearance the test will be immediately stopped and the subject will be dropped. Again, when any subject will complete the total test procedure (according to the exact protocol), he will be congratulated for good effort.

Vitamin and placebo administration

	Vitamin D₃	Placebo
Collection	Beximco Pharmaceuticals Limited, Bangladesh	Beximco Pharmaceuticals Limited, Bangladesh
Dose	80,000 IU/wk	80,000 IU/wk
Route	Oral	Oral
Ingredient	
• Cholecalciferol (40,000IU)• Microcrystalline Cellulose (58.1 gm)• Butylated Hydroxy Toluene (0.2mg)• Magnesium Stearate (3mg)• Gelatin Capsule Shell (1mg)	
• Microcrystalline Cellulose (303.8gm)• Butylated Hydroxy Toluene (0.2mg)• Magnesium Stearate (3mg)• Gelatin Capsule Shell (1mg)

STATISTICAL ANALYSIS

TITLE

**Effects of vitamin D₃ supplementation on lung functions and
exercise tolerance in D₃ deficient Asthma COPD Overlap
(ACO) patients**

Date: 06/09/2018

The results will be expressed as mean with standard error (mean \pm SE). The data will be statistically analyzed by Graphpad prism (Version 7) using independent sample 't' test (between two groups), paired Student's 't' test (between paired groups before and after intervention). Group comparisons will be done using one way ANOVA. Correlations between variables will be tested with Pearson correlation coefficient.

In the interpretation of results, ≤ 0.05 level of probability (p) will be accepted as significant.

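### The Methods table plans 60 patients (30 per group), but the protocol's own calculation gives 35 per group and its summary says 70; at 60, power for the planned difference is about 73%, not the implied 80%

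*Combined protocol and SAP*

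**What the plan says.** Three places in the combined protocol and SAP give the number of patients.

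- **Project Summary:** "For this study a total number 70 vitamin D₃ deficient" patients will be selected and then randomly divided into groups A and B.
- **Methods table:** "Sample size : 60". The Grouping rows give the control arm as "30 (thirty) D ₃ deficient ACO patients with placebo administration" and put the same number in the vitamin D₃ arm.
- **Sample size calculation:** a two-means formula with Zα = 1.96 and Zβ = 0.84 gives 34.257, taken as "approximately 35 for each group".

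Two further statements bear on the point. Study procedure says that a patient who does not follow the procedure exactly is dropped and "a new one will be included to fulfill the desired total sample number". The Statistical Analysis section names the between-group test as an "independent sample 't' test (between two groups"), with p ≤ 0.05 taken as significant. No dropout rate is given anywhere.

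**The concern.** The number to be randomised is a basic design quantity, and the protocol gives two values for it: 60 in the table, 70 in the summary and by calculation. The table entry does not look like a slip of one digit, since the total and both arms agree with each other and the arm sizes are also spelled out in words.

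The replacement rule makes this an operational problem. It tells staff to recruit until a desired total is reached, so that total has to be one number. As written, recruitment could stop at 60 or at 70 and either would comply with the protocol. That leaves the end of recruitment open to discretion after data have begun to accrue. If recruitment stops at 60, the trial has less power than its own calculation was meant to provide.

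**Working it through.** **Inputs, all from the Sample size calculation unless noted**

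- Means 364.1 (control) and 357.3 (study), so the difference is 6.8.
- SDs 7.21 and 12.25, so the sum of variances is 51.9841 + 150.0625 = 202.0466.
- Zα = 1.96 (two-sided 0.05).
- Zβ = 0.84. No power percentage is written, but Φ(0.84) = 0.7995, so 80% is implied.
- Group size 30 (Methods table) or 35 (calculation).
- Test: independent-samples t test at 0.05 (Statistical Analysis).

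**Step 1. Reproduce the protocol's figure**

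n = (1.96 + 0.84)² × 202.0466 / 6.8² = 7.84 × 202.0466 / 46.24 = 1584.045 / 46.24 = 34.257, rounded up to 35 per group, or 70 in total. The protocol's arithmetic is correct and matches the Project Summary. It does not give 30.

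**Step 2. Power by the protocol's own normal formula**

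Power = Φ(6.8 / √(202.0466/n) − 1.96)

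- n = 30: standard error √(202.0466/30) = 2.595; 6.8/2.595 = 2.620; Φ(0.660) = 0.745.
- n = 35: standard error √(202.0466/35) = 2.403; 6.8/2.403 = 2.830; Φ(0.870) = 0.808.

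**Step 3. Power for the planned t test**

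This uses the non-central t distribution, two-sided 0.05, with the non-centrality parameters 2.620 and 2.830 from Step 2. The protocol does not say whether variances are pooled, so both forms are shown.

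| Per group | Normal formula | Pooled t | Welch t |
|---|---|---|---|
| 30 | 74.5% | 73.1% (df 58) | 72.8% (df 46.9) |
| 35 | 80.8% | 79.7% (df 68) | 79.4% (df 55.0) |

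Simulation with 200,000 trials per size agrees with the t-test columns to within about 0.2 percentage points.

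**Step 4. Difference detectable with 80% power at 30 per group**

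- Protocol's formula: 2.8 × √(202.0466/30) = 2.8 × 2.595 = 7.27.
- Pooled t: 7.39. Welch t: 7.42.

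All three exceed the 6.8 used for planning.

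**Step 5. Could 60 have another origin?**

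- *A one-sided test.* With one-sided 0.05 the same inputs give 28 per group, not 30, and the protocol uses 1.96.
- *70 less dropouts.* Going from 35 to 30 would need a loss of 5/35 = 14%. No such rate is stated, and the plan provides for replacement.
- *Rounding.* 34.257 does not round to 30.

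**The case against.** The strongest reply is that this is probably a stale table entry. Two of the three places agree on 70, the calculation is sound, and the power loss arises only if 60 is really meant. That is fair. The documents do not show which size is intended, so the power figures here are conditional. The ambiguity in the recruitment target remains either way.

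A second objection is that setting 73% against 80% mixes methods, since 73% comes from the t test and 80% from the normal formula. Compared like for like, power falls from 80.8% to 74.5% (normal), from 79.7% to 73.1% (pooled t) or from 79.4% to 72.8% (Welch). This stands as a point of presentation: the loss is 6 to 7 percentage points on any method, and power at 60 is best described as 73% to 75%. The t-test figure remains the relevant one for the analysis as planned.

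Third, the replacement rule refers to patients who fail to follow the procedure. The protocol also allows voluntary withdrawal and drops patients whose walk test is stopped, without mentioning replacement in either case. So a reading of 60 as the expected completers out of 70 is not strictly ruled out. It is unlikely, though: no text supports it, no attrition rate is given, and the Grouping rows describe 30 patients receiving each treatment, not 30 completing.

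**Conclusion.** The concern holds. The Methods table (60) contradicts the Sample size calculation (35 per group) and the Project Summary (70). All three are current text, and nothing in the text supplied reconciles them. The gap is 10 patients, 5 per group.

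If 60 is the intended size, power for a difference of 6.8 is 72.8% to 73.1% with the planned t test, or 74.5% by the protocol's formula, and 80% power is reached only at a difference of about 7.3 to 7.4. The chance of missing the planned difference is then about 27% with the t test, not the implied 20%. These figures take the protocol's means and SDs at face value and assume a two-sided 0.05 test. The inconsistency itself rests on no assumption, and it must be fixed because the replacement rule cannot be applied without a single target.

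**What to change.** State one sample size in all three places and in the replacement rule. There are two ways to do it.

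1. **Use 70.** Change the Methods table to 70 in total and 35 per group. This adds 10 patients relative to the table and none relative to the summary and calculation. It would help to note that power with the planned t test is then about 79.5%.
2. **Keep 60.** Change the Project Summary to 60. Revise the Sample size calculation to justify 30 per group, since its present inputs cannot return that number. State power as about 73% for a difference of 6.8, or 80% for about 7.3 to 7.4. This needs no extra patients, but the lower power must be declared.

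If 60 was meant as the number of completers, say so, and give the assumed attrition and how it fits with replacement.

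Three clarifications could go into the same edit; none affects the conclusion above.

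- Name the outcome and unit behind 364.1 and 357.3.
- Check the group labels. As written, the study mean is below the control mean. If a higher value is better (an assumption, as it would be for 6MWD), that runs against the hypothesis "Alternate: Vitamin D₃ supplementation improves lung functions and exercise tolerance in vitamin D deficient ACO patient". The formula squares the difference, so n and power do not change.
- Confirm from the cited source that 7.21 and 12.25 are SDs, since they are only 2.0% (7.21/364.1) and 3.4% (12.25/357.3) of their means. This is a query, not a claim of error.

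### The planning SDs of 7.21 and 12.25 are implausibly small for means near 360 of an unnamed outcome, so the 80% power claim needs checking against the source and restating for the number planned

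*Combined protocol and SAP*

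**What the plan says.** The section headed Sample size calculation uses the standard formula for comparing two means. It takes a control mean of 364.1, a study-group mean of 357.3, SDs of 7.21 and 12.25, and normal deviates of 1.96 and 0.84 (two-sided 5%, 80% power). The means and SDs are credited to a 2018 source, which is also cited for the spirometry, oximetry and walk-test procedures. The key line contains "7.21^2 + 12.25^2)] / (364.1 - 357.3)^2", and the result is "approximately 35 for each group". The section gives no outcome, unit, time point or source group size.

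Other parts of the document bear on this:
- The Project Summary plans 70 patients. The Methods table plans 60, with 30 per group.
- The alternate hypothesis is that supplementation improves lung function and exercise tolerance.
- On the walk test: "The walking course will be 30 meter in length which was marked every 3 meter".
- In Statistical Analysis: "The results will be expressed as mean with standard error".
- The data schedule (Appendix II) records 6-minute walk distance (6MWD) in metres and peak flow (PEFR) in L/s.

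**The concern.** A mean near 360 points to 6MWD in metres. On the trial's own data form the other lung function and exercise outcomes are volumes in litres, flows in L/s, percentages or Borg scores from 0 to 10. For 6MWD in patients with obstructive disease, between-patient SDs of 7 and 12 m are very small. Values of that size are easier to understand as standard errors of a mean, and this trial's own plan to present mean with standard error makes such a mix-up credible.

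The stated sample size and its 80% power rest on these two numbers. If they are standard errors, the true SDs are larger by the square root of the source group size, and the trial has little chance of detecting 6.8. A non-significant result could then be misread as evidence of no effect. Even if the SDs are correct, the 80% does not apply to the 30 per group in Methods.

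**Working it through.** **Inputs.** From Sample size calculation: means 364.1 and 357.3 (difference 6.8), SDs 7.21 and 12.25, deviates 1.96 and 0.84. From Methods: 30 per group. The source group size, m, is not in the documents, so it is an assumption and is varied from 5 to 40.

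**1. The plan's figure.** n = (1.96 + 0.84)² × (7.21² + 12.25²) / 6.8² = 7.84 × 202.0466 / 46.24 = 34.26, rounded up to 35. It reproduces.

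**2. Plausibility of the SDs.**
- Relative size: 7.21 / 364.1 = 2.0%; 12.25 / 357.3 = 3.4%.
- Control 95% range: 364.1 ± 1.96 × 7.21 = 350.0 to 378.2, a width of 28.
- Study-group 95% range: 357.3 ± 1.96 × 12.25 = 333.3 to 381.3, a width of 48.

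In metres, the control range is shorter than one 30 m course length; the study range is longer than one length but still narrow. If the outcome were instead PEFR in L/min, 7.21 / 60 = 0.12 L/s against a mean of 364.1 / 60 = 6.07 L/s, which is just as tight.

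**3. Power if the values are SDs.** The standard error of the difference is √(202.0466 / n). Power is from the noncentral t distribution with unequal variances, two-sided 5%.
- 35 per group: standard error 2.403, 6.8 / 2.403 = 2.83, power 79%.
- 30 per group: standard error 2.595, 6.8 / 2.595 = 2.62, power 73%.

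**4. Power if the values are standard errors.** SD = standard error × √m, so the variance sum becomes 202.0466 × m and the n needed for 6.8 becomes 34.257 × m. The difference detectable with 80% power is 2.8 × √(202.0466 × m / n). For example, with m = 10 and n = 35 it is 2.8 × √57.73 = 21.3.

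| Assumed m | SDs | Power for 6.8, 35 per group | Power for 6.8, 30 per group | Detectable, 35 per group | Detectable, 30 per group | n per group for 6.8 |
|---|---|---|---|---|---|---|
| 5 | 16.1 / 27.4 | 24% | 21% | 15 | 16 | 172 |
| 10 | 22.8 / 38.7 | 14% | 13% | 21 | 23 | 343 |
| 20 | 32.2 / 54.8 | 10% | 9% | 30 | 32 | 686 |
| 30 | 39.5 / 67.1 | 8% | 8% | 37 | 40 | 1028 |
| 40 | 45.6 / 77.5 | 7% | 7% | 43 | 46 | 1371 |

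**5. Direction.** 357.3 − 364.1 = −6.8, so the study group is below control. The formula squares the difference, so n is unaffected. But if higher is better, as it is for 6MWD, the planning difference is not the improvement that the alternate hypothesis describes.

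**The case against.** The strongest reply is that the protocol labels both values as SDs, uses them as SDs, and gets its sum right. Nothing in the documents calls them standard errors, and only the cited source could show it. That stands. A reader might infer that the trial has 7% to 14% power; the documents do not support saying so, because that range needs both the standard-error reading and an assumed source of 10 to 40 per group. With 5 per group the power would be about 24%.

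Other objections also stand in part:
- The outcome is inferred. The data form shows this trial's units, not the source's, and PEFR in L/min would also give a mean near 360. The spread would be implausible there too, so the query does not depend on 6MWD.
- It is tempting to say that everyone would finish within one corridor length. That uses only the narrower arm, and a 95% range is not everyone.
- The planned presentation of mean with standard error concerns this trial's results, not the source's. It makes a mix-up credible and proves nothing.
- The documents do not describe the source's patients, so a very homogeneous sample cannot be excluded.
- The sign of the difference does not change n. It does raise the question of what 6.8 represents, since the documents never present it as a target effect.

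**Conclusion.** This is an implausible and undocumented planning input, not an arithmetic error. Three things hold on the documents alone: the outcome, unit and time point are missing; the SDs are 2.0% and 3.4% of means near 360; and the planning difference has the study group lower. It also follows, even taking the SDs at face value, that power for 6.8 is 73% rather than 80% at the 30 per group in Methods.

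The larger loss is conditional. If the values are standard errors, power for 6.8 at 35 per group falls to between 24% (m = 5) and 7% (m = 40), and the difference detectable with 80% power rises to between 15 and 43 in the outcome's unit. Power is far below 80% at every source size tried, but whether the condition is met is unknown until the source is checked.

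**What to change.** 1. Check the source table. In Sample size calculation, state the outcome, unit, time point and source group size, and whether 7.21 and 12.25 are SDs or standard errors.
2. If they are standard errors, multiply each by the square root of the source group size.
3. Reconcile 30 and 35 per group (60 and 70 in total). For that number, restate either the power for 6.8 or the difference detectable with 80% power. This is needed on either reading if 30 per group is kept.
4. Explain the direction of the planning difference, or replace it with one in the direction of the hypothesis.

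This does not call for a larger trial. On the standard-error reading, 80% power for 6.8 would need 172 to 1371 per group under the assumed source sizes, and nothing in the documents makes 6.8 a difference that must be detected. Stating what the planned number can detect is enough.

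The cost is one check of the source and a rewritten paragraph. The downside is a less favourable stated power. If the source confirms true SDs, the sponsor has documented an input that readers would otherwise question.
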